Participants who take psychotropic medications will be asked to remain consistent on the seven days of the trial (i.e., choose to take or not take medications each day that the VR headset is used). The general course of such medication involves such decisions daily, so participants will have received medical consultation from their prescribing physician outside of the context of the study. Participants who have questions about stopping medication will not be advised by the study staff. They will be encouraged to discuss with their prescribing physician. While participating in the VR intervention, they will be wearing a VR headset while completing homework and studying on a laptop. 40 minutes of each session are devoted to work completion. Participants may be offered to complete all 40 minutes at once or to take a 10-minute break. If a session does not meet a 45-minute threshold, the participant will be scheduled to repeat the session.

Initial evaluation: Participants in each phase will complete an initial diagnostic evaluation to confirm eligibility and collect baseline data. The first half of the evaluation will be done via electronic surveys hosted by Rutgers. Subjects will provide contact, demographic, and background information. To measure current symptoms of ADHD and inform diagnosis, they will complete the Barkley Adult ADHD Rating Scale (BAARS-Self). To capture potential risk factors for use of the VR system, prescreening questions will ask about related medical history. To evaluate other services and treatments participants may be receiving, they will complete the Service Utilization for College Student's Questionnaire. To obtain a baseline of treatment targets/mechanisms, participants will complete the Adult Concentration Index, Homework Motivation, and Homework Effort/Efficiency ratings. To measure potential treatment moderators and outcomes, subjects will complete the GAD-7 and PHQ-9, Columbia Suicide Severity Index (CSSI), BDEFS, BFIS, and surveys on Academic Record (self-report only; and GPA & Percentage

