VR intervention: After completing the initial evaluation and confirming eligibility, a new sample of 45 participants will be randomized to 1 of 3 groups and then scheduled to use the VR headset in their room/home or the library. Randomization will be performed (1:1:1) to the three conditions. Randomization will be blocked on ADHD medication status to ensure an equal number of participants taking and not taking ADHD medication in each group. Phase 3 includes a 2-session baseline where all participants complete homework and study outside of VR (total of 12 sessions; 2 non-VR baseline and 10 in VR condition). During each session, participants will complete a set of standardized reading comprehension problems to determine how many they complete and how accurately. LSU and Rutgers study staff will run VR intervention visits at their respective study sites.

Group 1, VR passthrough: After completing the two session non-VR baseline, participants will use the VR headset in their room/home or the library 10 times over three weeks (max twice a day with a minimum 2-hour break) for 1-hour sessions each time. The participant will wear the headset, but it will not be used as usual. The headset will be in “VR passthrough” mode, meaning the participant will see through to the normal environment and laptop (i.e., they can see the real world around them, just wearing a headset).

Group 2, VR environment only: After completing the two session non-VR baseline, participants will use the VR headset in their room/home or the library 10 times over three weeks (max twice a day with a minimum 2-hour break) for 1-hour sessions each time. The participant will wear the VR headset and engage in homework in the VR environment.

Group 2, VR environment + contingency management: After completing the two session non-VR baseline, participants will use the VR headset in their room/home or the 10 times

over three weeks (max twice a day with a minimum 2-hour break) for 1-hour sessions each time. The participant will wear the VR headset and engage in homework in the VR environment while receiving contingency management (real-time feedback on performance through red or green light FlowLight icon).

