4.6 Economic Burden and/or Compensation for Subjects

A. Expenses

Subjects will not be charged for their participation in this study, including the assessment and treatment sessions.

B. Compensation/Incentives

PHASE 1.

- Subjects will be paid \$40 for completion of all the baseline inclusion/exclusion measures and the SCID interview.
- Participants will be paid \$110 for completion of the intervention and all of the post-intervention measures. This is appropriate given that participants are devoting 1 hour of time 10 times over two weeks (max twice a day with a minimum 2-hour break) and 45 minutes for the outcomes questionnaires and follow-up phone interview.

PHASE 2.

- Subjects will be paid \$40 for completion of all the baseline inclusion/exclusion measures and the SCID interview.
- Participants will be paid \$110 for completion of the intervention and all of the post-intervention measures. This is appropriate given that participants are devoting 1 hour of time 10 times over two weeks (max twice a day with a minimum 2-hour break).. They will receive an additional \$25 gift card for participation in the focus group.

PHASE 3 and PHASE 4.

- Subjects will be paid \$40 for completion of all the baseline inclusion/exclusion measures and the SCID interview.
- Participants will be paid \$110 for completion of the intervention and all of the post-intervention measures in two parts: \$60 after completing 7 sessions within 2 weeks, and an additional \$50 after they complete all 12 sessions within 3 weeks. Payment will happen at the end of the study participation period of 3 weeks as a single e-gift card. This is appropriate given that participants are devoting 1 hour of time 12 times over three weeks (max twice a day with a minimum 2-hour break).
- Participants in the VR + feedback group will be paid up to \$130 if they maintain at least a 25% increase in focus over their baseline sessions 1 & 2 for a \$10 bonus. They can receive this bonus at the end of 7 sessions based on performance up to that point, and then again at the end of 12 sessions for a total reward compensation of \$20.
- They will receive an additional \$25 gift card for completion of follow-up measures 3 months post the final treatment session.

C. Compensation Documentation

E-gift cards will be sent electronically (i.e., a code will be emailed to participants, no emails will be given directly to the company [e.g. Amazon]). A record of codes sent to subjects will be kept.

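### Blocking on an undefined and untimed ADHD medication status cannot ensure the stated equality in students taking medication, because session-day use is left to the student; the Phase 4 model also names no term for the blocking factor.

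*Combined protocol and SAP*

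**What the plan says.** Section 1.3 A (Phase 3, VR intervention) places allocation after the initial evaluation: "After completing the initial evaluation and confirming eligibility, a new sample of 45 participants will be randomized to 1 of 3 groups". It continues: "Randomization will be performed (1:1:1) to the three conditions", and then "Randomization will be blocked on ADHD medication status to ensure an equal number of participants taking and not taking ADHD medication in each group". The Phase 4 paragraph adopts the Phase 3 procedures with 252 students, which is 84 per arm in section 1.5.

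The general procedures in section 1.3 A deal with medication on session days: "Participants who take psychotropic medications will be asked to remain consistent on the seven days of the trial". The parenthesis that follows explains consistency as a decision to "choose to take or not take medications each day that the VR headset is used". The next sentence adds: "The general course of such medication involves such decisions daily". The Phase 3 text gives a "total of 12 sessions; 2 non-VR baseline and 10 in VR condition".

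For Phases 3 and 4, section 1.3 B lists a Current Day Medication Adherence survey and the Service Utilization questionnaire at the initial evaluation, and the adherence item again at each session. Neither is linked to the blocking factor. The Intent to Treat paragraph of section 6.1 names condition, time and their interaction as fixed effects. The only stated route for a further covariate into the final model is an association with missing data.

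**The concern.** The purpose given for blocking is equality between arms in who is taking ADHD medication. The use that could affect a session's outcome is use on that day. The plan treats this as the student's own choice and does not say whether that choice is known before allocation. If the blocked variable is something else, such as having a prescription or having taken medication on the day of the evaluation, the equality does not follow.

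Two related gaps add to this. The consistency request refers to seven days and to days with the headset, while Phases 3 and 4 have 12 sessions, of which the first 2 are outside VR. Read literally, it does not cover the baseline sessions. And a factor considered important enough to block on is absent from the analysis model, so any precision that blocking gains is not carried into the standard errors.

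**Working it through.** The plan gives no figure on this point to reproduce. The check has two parts.

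**Order of events.** Initial evaluation, then randomisation, then 2 sessions outside VR, then 10 headset sessions. Three readings of medication status are possible at the time of randomisation:

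- (a) receiving ADHD medication;
- (b) having taken it on the day of the evaluation;
- (c) intending to take it on session days.

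The listed instruments could supply (a) or (b). None is described as recording (c). Only (c), combined with students keeping to their intention, delivers equality in session-day use.

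**Size of the shortfall under reading (a).**

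Inputs from the plan: n = 84 per arm in Phase 4 and 15 per arm in Phase 3.

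Inputs assumed, because the plan states neither: share medicated m (0.3 to 0.7) and session-day uptake among the medicated q (0.5 to 0.9), the same in every arm.

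With complete blocks, each arm holds k = n × m medicated students, and takers per arm follow Binomial(k, q). Without blocking they follow Binomial(n, m × q).

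For Phase 4 with m = 0.5 and q = 0.7, so k = 42:

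- Blocked: SD of the between-arm difference = √(2 × 42 × 0.7 × 0.3) = √17.64 = 4.2 students. The 95% range is 1.96 × 4.2 = 8.2 students, and 8.2/84 = 9.8 percentage points.
- Unblocked: m × q = 0.35, so SD = √(2 × 84 × 0.35 × 0.65) = √38.22 = 6.2 students.
- Ratio of variances: 17.64/38.22 = 0.46.

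Exact binomial results for Phase 4 with m = 0.5:

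| q | SD blocked | SD unblocked | P(equal), blocked | P(gap ≥ 10 points), blocked | Same, unblocked |
|---|---|---|---|---|---|
| 0.5 | 4.6 | 5.6 | 9% | 6% | 13% |
| 0.7 | 4.2 | 6.2 | 10% | 4% | 17% |
| 0.9 | 2.8 | 6.5 | 15% | 0.2% | 19% |
| 1.0 | 0 | 6.5 | 100% | 0% | 19% |

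Over m = 0.3 to 0.7 and q = 0.5 to 0.9, the chance of a gap of 10 points or more in Phase 4 runs from below 0.1% to 12% with blocking. The blocked variance is 14% to 77% of the unblocked variance.

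In Phase 3, 10 points is 1.5 students, so a difference of 2 is enough. Over the same grid (k rounded to whole students) the chance is 7% to 50% with blocking and 44% to 58% without. At m = 0.5 and q = 0.7 it is 41% against 57%.

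The row q = 1.0 is the only one in which the stated equality holds. It also describes what happens within the will-take stratum if blocking is on a declared intention that students keep.

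**The case against.** The strongest reply is that the plan never says the blocking factor is prescription or enrolment status. Its purpose clause speaks of taking and not taking, a medication item is collected before randomisation, and students are asked to be consistent. If status means the intended session-day choice, most of the conflict disappears. This stands in part: the defect is an undefined and untimed factor, not a factor known to be wrong. The sponsor still has to say which it is.

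It is also fair that blocking does most of its job at 84 per arm. A remaining chance imbalance is ordinary random variation of the kind the standard error reflects. Where sessions 1 and 2 serve as the baseline, a constant medication choice is present at both ends, and its constant effect drops out of the change. The plan does not say which baseline applies to each outcome.

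A reader might infer something stronger: that the arms will differ systematically because only the feedback arm is offered a bonus "if they maintain at least a 25% increase in focus over their baseline sessions 1 & 2" (section 4.6 B). The documents do not support that as a finding. A student who takes medication at every session also has a medicated baseline and gains no obvious advantage. The bonus favours medication only if use changes between baseline and later sessions, and nothing shows that students would do this. If they did, for example a 10-point shift among 42 medicated students (4.2 students), it would be a post-randomisation effect retained in the intent-to-treat contrast, not a failure of allocation. Declaring an intention beforehand would not prevent it.

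**Conclusion.** The concern holds in a limited form. As written, blocking does not support the claim of equal numbers taking ADHD medication in each group. It gives partial balance in session-day use unless the blocked variable is the session-day intention and students keep to it.

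On the assumed inputs (half medicated, 70% uptake, equal across arms), the Phase 4 difference in takers has SD 4.2 students, and a gap of 10 points has about a 4% chance instead of 17% without blocking. This is some loss of precision. It should not be read as bias in the contrast, and since the plan gives no medication effect it cannot be converted to an effect size without a further assumption. The shortfall is larger in Phase 3, whose purpose is to estimate effect sizes from 15 per arm.

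The missing model term is a separate gap that does not depend on these assumptions.

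**What to change.** 1. Define the blocking variable and when it is recorded. At the initial evaluation, before allocation, ask each medicated student which session-day choice they intend under the existing consistency request. Staff record the answer and give no advice. Form the levels from it: not on ADHD medication, on it and intending to take it, on it and not intending to take it.
2. Collapse levels where strata are too small. With the assumed inputs the last level holds 45 × 0.5 × 0.3 = 6.75 students in Phase 3, about 2 per arm, so collapsing is likely there. In Phase 4 it holds 252 × 0.5 × 0.3 = 37.8, about 13 per arm.
3. Include the blocking factor as a baseline fixed effect, with its interaction with time, in the Phase 4 mixed model. The interaction is needed because the contrast of interest is a difference in change.
4. Report per-session adherence by arm descriptively. Keep it out of the primary model, because it is measured after randomisation.
5. Replace the claim of ensured equality with a statement of what is balanced.
6. Reconcile the seven days with the 12 sessions, state whether the consistency request covers the 2 sessions outside VR, and reconcile psychotropic medication in the consistency request with ADHD medication in the blocking sentence.

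The cost is one added question, slightly more incomplete blocks and a model term. No visits or participants are added. These changes would not remove any arm-driven change in use after allocation; item 4 would only make it visible.

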In-Session Assessment: As with Phases 1 and 2, participants will first complete 10 minutes of standardized reading comprehension passages and questions before being automatically prompted on their VR screen to complete 40 minutes of studying in either pass-through, VR immersive mode, or VR immersive mode with contingency management. After the allotted 40 minutes, participants will then be asked to complete 10 minutes of brief rating scales asking about feasibility/usability of using VR to complete work, attention/concentration, and homework effort. Specifically, participants will complete the Adult Concentration Inventory, the Homework Motivation Index, and the Homework Effort Index each session. Finally, they will answer a question about whether or not they took ADHD medication that day – the Current Day Medication Adherence. Participants will complete the 10-item Systems Usability Scale after sessions 4 and 12 only.

Outcome Assessment: Following the 12th session, participants will complete an outcome assessment. For the outcome assessment, they will complete some of the same outcome battery described in Phase 1 and 2 (BAARS-Self, BDEFS, BFIS, Academic Records, GPA & Percentage of Assignments Completed). Questions on feasibility and usability of the VR system will be asked in the outcome assessment. Outcome assessments will be performed by Rutgers study staff using Rutgers-hosted REDCap.

Follow-Up Assessment: Three months after the completion of the final session, participants will complete a follow-up assessment visit. The assessment battery will be the same as the outcome battery described in the initial outcome assessment. Follow-up assessments will be performed by Rutgers study staff using Rutgers-hosted REDCap.

PHASE 4: Conduct a larger parallel group randomized trial.

Phase 4 will follow the same procedures as Phase 3 (see above) except instead of n=45, we will randomize n=252 (note, number who consent is higher, to account for those found not eligible after consenting). This will be done across several cohorts. Please see the study timeline figure in section 1.10 for a visual of how many subjects will be in each cohort.

B. Data Points

PHASE 1: Refine objective data capture techniques.

Initial evaluation:

- Contact, demographic, and background information
- Service Utilization for College Students
- Current Day Medication Adherence survey
- BAARS-Self
- Pre-screening questions
- Adult Concentration Index (ACI)
- RCADS

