Within 6 months of the conclusion of the participation in the intervention, participants will participate in a focus group. The focus group will take approximately 90 minutes.

PHASE 3:

Each participant will be involved for approximately 18 weeks (1 week of initial evaluation, 1 week of intervention baseline, 3 weeks of intervention, 1 week of outcome assessment, then a 3-month follow-up).

The initial evaluation will take approximately 1.5 hours.

Each VR intervention session will take approximately 1 hour (10 minutes of reading comprehension questions, 40 minutes of intervention, 10 minutes to complete surveys). Across the intervention, they will complete 12 1-hour sessions (2 baseline without VR headsets, 10 in the assigned condition).

The outcome assessments will take approximately 30 minutes.

The 3-month follow-up will take approximately 20 minutes to complete.

PHASE 4:

Each participant will be involved for approximately 18 weeks (1 week of initial evaluation, 1 week of intervention baseline, 2 weeks of intervention, 1 week of outcome assessment, then a 3-month follow-up).

The initial evaluation will take approximately 1.5 hours.

Each VR intervention session will take approximately 1 hour (10 minutes of reading comprehension questions, 40 minutes of intervention, 10 minutes to complete surveys). Across the intervention, they will complete 12 1-hour sessions (2 baseline without VR headsets, and 10 in the assigned condition).

The outcome assessments will take approximately 30 minutes.

The 3-month follow-up will take approximately 20 minutes to complete.

D. Endpoints

Participants will be removed from the study if they have an adverse reaction to the VR headset, such as nausea or dizziness, that taking breaks and making adjustments to the VR headset is not able to address.

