2.3 Other Resources

In the event that a subject finds the assessments and/or intervention mildly anxiety provoking, research staff members will express empathy and appropriate encouragement and reassurance. Risk of emotional distress will be minimized through effective rapport building and interactions with the subjects. A small percentage of subjects might initially feel disoriented or dizzy in the VR environment. Most subjects adjust quickly after taking a break or working in small chunks of time. Should discomfort become sufficient to pose distress for the subject, the research staff member will discuss these reactions to determine whether the subject wishes to continue completing the research procedures.

*Some of the questionnaires and interviews have items that ask about suicidality, and it is possible that subjects will endorse items pertaining to threat to self. These questionnaires are reviewed at their baseline assessment visit. If any items that endorsed suicidality or threat to self were checked by subjects, then the study staff will consult with the PI ([name], who is a licensed clinical psychologist) to complete a risk assessment to determine appropriate actions based on level of risk (e.g., presence of a plan, desire to act on the plan, and access to means to carry out the plan). (see 4.7E for protocol for steps following risk assessment).

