Phase 2: This project incorporates the contingency management procedures. Trends in motivation across sessions will be evaluated in relation to objective and rating scale metrics of attention and to FlowLight data. Focus groups will be audio-recorded and transcribed verbatim. The focus group data will be analyzed inductively for information relevant to feasibility and acceptability of the protocol. Two study personnel will separately code notes taken during the focus groups for emerging concepts and themes. Initial analysis will consist of identifying concepts found within the data through open coding. Inter-rater reliability checks will be used to compare the themes generated. Coding will continue until the point of saturation, that is, when no new concepts emerge. Data will be systematically analyzed according to the principles of thematic analysis, a method commonly used in qualitative research of this nature.

Phase 3. Because these analyses will focus on evaluating preliminary intervention effect sizes, outcome analyses will be conducted separately for each target mechanism. To compare groups, the variable (e.g., objective attention) will be entered analysis of variance (ANOVA), which will yield effect sizes for time and for interactions of time by intervention. The primary dependent variables will be objective assessment of attention and ratings of concentration, as well as ratings of homework effort and homework motivation. We will also compare trajectories of objective attention data across the three conditions.

Phase 4. The mixed model methodology planned and incorporated by the SAS GLIMMIX procedure can accommodate missing response data, thus allowing us to make use of all available data; note that covariate measurements are taken at baseline and should not be missing. Using Bayes' estimation, individuals with more data are given more weight in the calculation. This procedure is preferable in comparison to listwise or pairwise deletion in analyses where portions of the developmental curve are represented by differing individuals. In addition, we will check to see whether missing observations are missing at random, where we will test whether treatment group or any other covariate has an effect on the missing information. Any covariate associated with missing data will be included in the final model. Mediational models

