analyzed using MPlus will address missing data using full information maximum likelihood estimates. This approach makes full use of available data and is one of several procedures considered the state of the art for addressing missing data.

Intent to Treat Analysis: An intent-to-treat approach will be used to analyze the data, wherein each participant will be kept in the group to which they were randomized for analysis, regardless of treatment compliance. A mixed-effects model will be used to account for the repeated-measure nature of the study design. Time will be treated as a dummy-coded categorical variable using baseline as the reference. A student-level random effect will be included and modeled using an auto-regressive covariance structure to account for within-subject dependence due to repeated measurements. The models will also include treatment condition as a student-level fixed effect, and condition x time interaction effects. This modeling will allow us to compare baseline to 8-week (post) changes, and the extent to which these changes differ across conditions.

Mediator Analyses: Mediational analyses will be conducted using structural equation modeling. There are advantages of a structural equation modeling approach to estimating and determining the significance of indirect effects within mediational models and outlined specific estimation procedures that are available in MPlus. All analyses will be conducted in MPlus which provides estimates that partition the total effect of an independent variable on a dependent variable into the direct and indirect effects using bootstrap estimation procedures. Preliminary analyses will be conducted separately for each mediator. Scores on the mediator will be modeled as a function of pretest scores on the mediator, intervention condition, and covariates. The intervention's effect can then be partitioned into the direct effect on changes (e.g., on school grades) at posttest and follow-ups and the indirect effects via the mediator. These initial analyses will be used to guide a more comprehensive model that will incorporate mediators that emerge as significant within the individual models. Primary mediation analyses will focus on whether change in the proposed mechanisms of action mediates improvement in AIM total scores and BDEFS.

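### Section 1.3 D takes participants with an unresolved headset reaction out of the study, so their post and 3-month functioning outcomes in Phase 4 would go uncollected; the bias is probably small and the loss is cheap to avoid

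*Combined protocol and SAP*

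**What the plan says.** Section 1.3 D (Endpoints) sets one removal rule and makes no exception for the randomized phases: "Participants will be removed from the study if they have an adverse reaction to the VR headset, such as nausea or dizziness". It applies only to a reaction "that taking breaks and making adjustments to the VR headset is not able to address".

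The assessments in section 1.3 A depend on sessions. For Phase 3, "Following the 12th session, participants will complete an outcome assessment", and "Three months after the completion of the final session, participants will complete a follow-up assessment visit". These carry over: "Phase 4 will follow the same procedures as Phase 3 (see above) except instead of n=45, we will randomize n=252".

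Two other sections treat persistent discomfort differently. Section 2.3 has staff discuss the reaction with the participant to learn whether they want to carry on. Section 4.7 A (Risk 3) suspends the session and has staff discuss withdrawal as an option.

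Section 6.1 specifies intent-to-treat for Phase 4: "each participant will be kept in the group to which they were randomized for analysis, regardless of treatment compliance". Its mixed model "can accommodate missing response data, thus allowing us to make use of all available data". The plan tests whether arm or covariates predict missingness and adds those that do. It names no sensitivity analysis for data that are not missing at random.

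On frequency, section 2.3 says only: "A small percentage of subjects might initially feel disoriented or dizzy in the VR environment". It adds that most people adjust quickly.

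**The concern.** A participant who cannot tolerate the headset is someone an as-randomized comparison should include. Under 1.3 D that person leaves the study, not only the headset sessions, and never reaches session 12. No clause collects the functioning measures after an early stop. Section 1.3 B schedules these measures only at baseline, post and 3 months, so a removed participant contributes a baseline value and no observed change.

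The assigned equipment is what causes this missingness, and immersive and passthrough modes may differ in how well they are tolerated. At stake are the Phase 4 comparisons of immersive arms with passthrough on functioning. The comparison of VR plus contingency management with VR alone is not clearly affected, since both arms are immersive.

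**Working it through.** **Is there a clause that rescues the data?** Intent-to-treat in 6.1 governs which group a person is analysed in. It does not add data collection. The Phase 2 focus group is open to people who did not finish their VR sessions (1.3 A), but Phases 3 and 4 have no matching provision for outcomes. If the final session is read as the participant's own last session, a 3-month date exists, but removal from the study would still end follow-up.

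**Inputs from the plan.** 84 per arm, 252 in total, and planned effects of d = 0.4 and 0.8 (section 1.5). Section 1.5 states no alpha, sidedness or target power, so its sample size cannot be reproduced. I assume two-sided 0.05, unadjusted. An unpaired t-test with 84 vs 84 then has 73.1% power at d = 0.4.

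**Assumed inputs.** The plan gives no removal rate. Let p be the proportion removed in an arm. Let g be the residual deficit: how far, in SD, removed participants fall below what the model predicts for them. I take g as equal across arms.

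- Low case, closer to section 2.3: p = 2.5% in each immersive arm, 0.5% in passthrough.
- High case: p = 10% and 2%.

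**Participants affected.**

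- Low: 84 × (0.025 + 0.025 + 0.005) = 4.6, about 5.
- High: 84 × (0.10 + 0.10 + 0.02) = 18.5, about 18.

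**Bias.** The model overstates an arm's mean by p × g, so the bias in an immersive vs passthrough difference is (p_immersive − p_passthrough) × g.

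| Case | g = 0 | g = 0.3 | g = 0.8 |
|---|---|---|---|
| Low: difference 0.02 | 0 | 0.006 SD | 0.016 SD |
| High: difference 0.08 | 0 | 0.024 SD | 0.064 SD |

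At g = 0.8 these are 0.016/0.4 = 4% and 0.064/0.4 = 16% of the smaller planned effect. Equal removal with equal deficit gives zero. If passthrough loses more, the sign reverses.

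**Scale.** The standard error of a pairwise difference at 84 per arm is √(2/84) = 0.154 SD. The largest low-case bias is 0.016/0.154 = 0.10 of a standard error. The largest high-case bias is 0.064/0.154 = 0.41.

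**Power at d = 0.4.**

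- Low: 84 × 0.975 ≈ 82 vs 84 × 0.995 ≈ 84 retained gives 72.6%.
- High: 84 × 0.90 ≈ 76 vs 84 × 0.98 ≈ 82 retained gives 70.4%.

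The cost is 0.5 and 2.7 percentage points.

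**The case against.** The best counter-argument has four parts.

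- **Removal may not be mandatory.** Sections 2.3 and 4.7 A leave continuing to the participant. This stands in part. Non-collection is the plain reading of 1.3 D, but the document is not uniform, and a reader should not infer that every intolerant participant would be removed.
- **The effect is negligible.** All three arms wear a headset, section 4.1 C excludes people with vestibular or neurological problems that affect balance or gait, and section 2.3 expects most to adjust. The low-case bias is at most a tenth of a standard error, and no text supports the high case. This stands as to size. It does not make the loss harmless, because outcomes not collected cannot be recovered later.
- **The analysis already handles it.** The mixed model uses all available data and adds predictors of missingness. That suffices only under missing at random, and the planned check cannot show whether unobserved outcomes differ from the model's predictions.
- **Few outcomes benefit.** The outcomes in section 1.6 B (on-task behavior, concentration, motivation, effort) are measured in session, as are Phase 3's primary variables in 6.1. Phase 3 also aims at effect sizes, not tests (1.5). This stands, and it confines the point chiefly to Phase 4 functioning ratings.

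**Conclusion.** The point holds in limited form. As written, 1.3 D combined with session-triggered assessments loses post and 3-month functioning data from randomized participants for a treatment-related reason that can be avoided. Sections 2.3 and 4.7 A conflict with it.

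The bias is probably small: 0 to 0.016 SD under low assumed rates and up to about 0.06 SD under high ones. Its direction depends on which arms lose more and on how removed participants actually fare. All rates and deficits are assumptions. The case for change rests on low cost, not on a large expected bias.

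Two stronger readings are tempting and not supported. One is that the rule breaches intent-to-treat. It does not: 6.1 keeps these participants in their randomized arm with the data already collected. The other is that the Phase 4 comparisons are seriously compromised. Nothing in the documents suggests removals frequent or unequal enough for that.

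**What to change.** Reword 1.3 D so that an unresolved reaction means permanent discontinuation of headset sessions, under the same safety rule and in line with sections 2.3 and 4.7 A, with the participant staying in the study unless consent is withdrawn. Then:

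- Send the REDCap post battery to these and any other early stoppers at the planned post time for their cohort, counted from session 1, and the 3-month battery three months after that. The session-12 trigger misses anyone who stops early for any reason. Session 1 is a sound anchor because it precedes headset use in every arm (1.3 A).
- State that post time explicitly. The plan gives different lengths: 1 + 2 = 3 weeks of Phase 4 sessions in 1.3 C, 6 weeks in the Phase 4 summary in 1.3, and an 8-week post point in 6.1.
- Include the data in the intent-to-treat model and report headset discontinuations by arm.

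**Cost.** A protocol and consent wording change, a date trigger, and a payment rule, because section 4.6 B ties the $110 to completing 7 and 12 sessions. Assuming $25 for the post battery plus the existing $25 follow-up card, the headset-reaction group costs 5 × $50 = $250 in the low case and 18 × $50 = $900 in the high case. Other early stoppers would add to this. No new measure is needed, and the batteries take about 30 and 20 minutes (1.3 C).

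**Limits.** Timing will match completers only approximately, since section 1.10 allows a month for make-up sessions. Missing at random is still needed for those who do not respond. In-session outcomes, including Phase 3's primary variables, are not recovered.
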